7.4.4 Post Treatment (V7) Visit

The following procedures will occur at the Post Treatment visit (V7), which should be scheduled 12 weeks ± 4 days from the last dose of study medication. The V7 visit can occur simultaneously with the 8 week Follow-up Visit for the infant (iV1). This is the last scheduled clinic visit for the maternal participant.

Table 8: Post Treatment (V7)

Visit 7 (V7) Post Treatment Visit	
Component	Procedures
Administrative and Regulatory	
 • Review/update locator information • Visit questionnaire • Provide reimbursement • Record/update AEs
Behavioral	
 • Protocol adherence counseling
Clinical	
 • Review/update medical history • Review/update concomitant medications • Perform modified physical examination • Provide available test results from delivery, as applicable
Laboratory	
 • Collect blood 
 • CBC with platelets and differential • Hepatic function panel (AST, ALT, albumin, total and direct bilirubin, alkaline phosphatase) • PT/INR • Creatinine • Lipase • Creatinine kinase • HCV RNA viral load • HCV resistance testing *

*If HCV RNA is detectable, the participant would be asked to return to have HCV resistance testing done, and HCV resistance testing should be done if the participant is still on study medication at time of delivery and study medication was discontinued at the delivery visit because the participant was planning to breastfeed.

7.4.5 Infant Follow-Up Visits (iV1, iV2, iV3)

After delivery, infants will be seen at the following time points:

iV1: 8 weeks \pm 6 weeks

iV2: 6 months \pm 2 weeks

iV3: 12 months \pm 2 weeks

The following procedures will occur at the Infant Follow-Up Visits (iV1, iV2, iV3). If blood sampling is not possible, then the results can be collected from the infant's medical record if available. Results of physical and developmental exams will be shared with the mother, and if necessary with the infant's routine healthcare provider. Referrals will be made as necessary.

Table 9: Infant Follow-Up Visits (iV1, iV2, iV3)

Visit iV1, iV2, iV3 Infant Follow-Up Visits	
Component	Procedures
Administrative and Regulatory	
• Review/update locator information• Review infant demographics (iV1)• Sign release(s) for medical records for infant• Provide reimbursement• Schedule next visit (iV1, iV2)• Record/update AE's• Document pre-existing conditions (iV1)
Clinical	
• Review/update medical history***• Review/update concomitant medications***• Growth assessment including weight, length, and head circumference***• Perform age appropriate physical examination• Developmental Exam[^] (iV2 and iV3 only); discuss results with mother, routine healthcare provider if needed and provide referrals (i.e. early intervention) if necessary• Provide available test results as applicable (i.e. HCV RNA test)
Laboratory	
• Collect infant blood
• HCV RNA (iV1, iV2, and as applicable at iV3)*• HCV resistance testing (if HCV RNA is detectable)**

[^]To include an age appropriate developmental exam, Bayley Scales of Infant and Toddler Development, and a general developmental screening tool completed by parents, Ages and Stages Questionnaire (ASQ). These evaluations will be done/reviewed by a qualified individual.

*If HCV RNA is detectable at iV1 or iV2, the infant would also have an HCV RNA performed at iV3. If HCV RNA is non-detectable/negative at both iV1 and iV2, no additional samples are needed. If infant sample is unable to be collected at iV1 and/or iV2, a sample may be collected at iV3.

**If HCV RNA is detectable at iV1 or iV2, the infant would need to return to have HCV resistance testing.

***May be collected from the medical record as applicable

7.5 Follow-up Procedures for Participants Who Permanently Discontinue Study Medication

Participants will be permanently discontinued for significant laboratory abnormalities or adverse events as outlined in section 9.3 and 9.4 or if they choose to discontinue the study medication. If participants miss greater than one dose per week (averaged over the duration of the study) they may be discontinued at the discretion of the Protocol Chair/Principal Investigator. Participants who are permanently discontinued from the study will be instructed to return the study medication and study medication

log. All protocol-specified study procedures may continue for safety except the following:

- Provision of study medication
- Provision of medication use adherence counseling

The following procedures will be performed at the visit in which study medication use is permanently discontinued:

- Collection of blood for PK analysis (single time point)
- HCV resistance testing
- Viral load as needed (i.e. participant withdraws, investigator opinion)
- Medical history review
- Concomitant medication review
- Brief physical examination including vital signs, if indicated.

The participant will be asked to continue in the study and complete all remaining scheduled maternal and infant visits per protocol for safety.

7.5.1 Interim Visits

Interim visits may be performed at any time during the study. Study procedures may be repeated at interim visits as deemed clinically indicated. All interim contacts and visits will be documented in participants' study records and on applicable CRFs.

7.6 Pharmacokinetics

All enrolled participants will undergo intensive serum PK specimen collection procedures at the PK1 and PK3 visits. These collections will occur at study visits as described in Table 9.

Table 9: SOF and VEL PK Sampling

Time since SOF/VEL*	Plasma Sample	Timed Meal	SOF/VEL PK sample (mL)	Protein Binding (mL)	PBMC/DBS sample (mL)	Total blood (mL)
predose	+		4	0	4	8
DOSING		+				
30 mins	+		4	0	0	4
1 hour	+		4	0	0	4
2 hours	+		4	6	0	10
3 hours	+		4	0	0	4
4 hours	+		4	0	0	4
5 hours	+		4	0	0	4
8 hours	+		4	0	0	4
12 hours	+		4	0	0	4
24 hours	+		4	0	0	4

*Time listed is the target time for PK sample. If a sample is collected prior to next scheduled PK sample it will not be considered a protocol deviation. Only missed samples will be considered protocol deviations.

Participants will be instructed to bring their daily dose of SOF/VEL to the visits requiring intensive PK sampling (PK1 and PK3 visits) for timed administration. If they do not bring their dose, then a dose of study medication can be dispensed from the pharmacy/PoR/designee. Intravenous catheters may be placed during intensive PK visits. A pre-dose sample will be collected. Study drug will be administered as close as possible to the participant's normal dose time if possible and within 5 minutes of completing and within 30 minutes of initiating a standardized moderate-fat-calorie breakfast (~600 calories and 25 to 30% fat) following an overnight fast (no food or liquids, except water, for at least 8 hours). Participants will be restricted from food intake until after collection of the 4 hour blood draw and restricted from water consumption 1 hour before and 2 hours after dosing, except for approximately 240 mL of water given with study drug and standardized meal. Whole blood will be collected into appropriate sized Vacutainer® Plus plastic sterile tube(s) with K₂EDTA (spray dried) additive. Immediately after collection, the collection tube will be inverted 8 to 10 times to allow mixing with the anticoagulant. Further processing instructions can be found in the Specimen Collection and Procedures Manual.

For the PK2 visit (sparse PK visit), a single 8mL blood sample (PK and PBMCs) will be drawn noting the time of the collection and the time at which the participant took their previous SOF/VEL dose.

7.7 Adherence Counseling and Assessment

Adherence counseling to the study protocol will be performed at each study visit. Additionally, investigators may use text messaging (daily or weekly), follow-up phone calls, email, and/or meeting study participants at their regular clinic visits in order to improve adherence to the study medication and procedures. All options will be included in the informed consent document and will be tailored to the participant's needs. At the follow-up visits (PK1, PK2, PK3 and End of Treatment Visit), all remaining medication will be counted, recorded and returned to the pharmacy. Study participants will be given a medication administration log and also may be instructed on the use of photo/video capture of study medication administration using an IRB approved and secure mechanism to assist in study medication adherence. Participants will take a photo/video of themselves when taking their study medication daily through an IRB approved mechanism and send the photo/video via text to the ID research designated study smart phone or the photos/videos may also be reviewed during study visits. The provided paper log will have instructions on how and when to take the medication. Research staff will recommend that participants take the study medication consistently at a time convenient for their schedule, preferably in the morning. If a participant forgets to take a dose, she should take the missed dose as soon as she remembers but should not take more than one tablet of SOF/VEL per day. Directions on how to store the medication as well as what to do if the medication is lost or stolen will be given to the participant and included on the medication administration log as applicable. Participants will be asked to bring the medication

administration log to the next study visit for review. Medication administration logs will be collected at the next visit and a new log (as applicable) will be given with each bottle/refill of study medication. The completed logs will be compared to the photos/videos, as available. Adherence counseling will be performed at the following visits: enrollment, PK1, PK2, and PK3 (and at delivery if the participant has not completed the 12 weeks of study medication and is not breastfeeding).

7.8 Clinical Evaluations and Procedures

Physical exams will include the following assessments:

- General appearance
- Weight
- Vital signs
 - Temperature
 - Pulse
 - Blood pressure
 - Respirations
- Height^
- Abdomen*
- Head, Eye, Ear, Nose and Throat (HEENT) Examination*
- Lymph nodes*
- Neck*
- Heart*
- Lungs*
- Extremities*
- Skin*
- Neurological*

^obtained at Screening Visit only

*may be omitted after the Enrollment Visit

Additional clinical assessments may be performed at the discretion of the examining clinician in response to symptoms or illnesses present at the time of the exam.

7.9 Laboratory Evaluations

Local Laboratory (UPMC Clinical Laboratory)

- Blood
 - HIV serology
 - Hepatitis B Virus testing
 - HBsAg
 - Anti-HBc
 - Anti-HBs
 - PT/INR
 - Lipase
 - Creatine kinase
 - HCV RNA viral load: Maternal and Infant
 - Hepatitis C genotype (as required at screening)
 - CBC with differential and platelets
 - Creatinine
 - Hepatic function panel
 - AST
 - ALT
 - Albumin
 - Total and direct bilirubin
 - Alkaline phosphatase

Outside Laboratory

- Blood
 - Blood PK for SOF and VEL(University of Colorado)
 - Dried Blood Spots and Peripheral Blood Mononuclear Cells for intracellular concentrations of the active SOF metabolite (GS-461230) (University of Colorado)
 - Protein Binding Assay (University of Colorado)
 - HCV Resistance Testing (Quest Lab)

7.10 In Depth Interviews

At the screening visit and the end of treatment visit a trained interviewer from the Qual EASE team (CHRC Data Center, University of Pittsburgh) will conduct an in- depth interview about Hepatitis C infection, risks of perinatal transmission, concerns about treatment during pregnancy and drug research during pregnancy. The interviewer will use the HIP Script to conduct the interview. All interviews will be recorded and transcribed verbatim. The original recordings will be destroyed after transcription. The interview may be conducted at the visit or prior to the next visit via phone or a secure video conferencing system.

7.11 Specimen Collection and Processing

The study site will adhere to the standards of good clinical laboratory practice and standard operating procedures for proper collection, processing, labeling, transport, and storage of specimens. Specimens for SOF/VEL PK analysis and protein binding

will be transported from the Clinical Research site to the Magee-Womens Research Institute Microbiology Laboratory for storage until they are shipped to the appropriate laboratory for processing and analysis. The samples will be shipped when arranged with the respective laboratories listed for PK analysis and protein binding.

7.12 Biohazard Containment

As the transmission of hepatitis C and other blood-borne pathogens can occur through contact with contaminated needles, blood, and blood medications, appropriate blood and secretion precautions will be employed by all personnel during blood draws and transport, shipping and handling of all specimens for this study as recommended by the CDC and National Institutes of Health (NIH). All biological specimens will be shipped using packaging mandated by Code of Federal Regulations (CFR) 42 Part 72. All dangerous goods materials, including diagnostic specimens and infectious substances, must be shipped according to instructions detailed in the International Air Transport Association (IATA) Dangerous Goods Regulations. Biohazardous waste will be contained according to institutional, transportation/carrier, and all other applicable regulations.

8 ASSESSMENT OF SAFETY

8.1 Safety Monitoring

Study investigators are responsible for continuous close safety monitoring of all study participants, and for notifying Gilead Sciences if unexpected and/or serious events occur. Two independent physician safety monitors, who are not otherwise involved in the study will review the safety data once per month or more frequently as needed throughout the period of study implementation, discuss study medication management, and address any potential safety concerns.

8.2 Clinical Data and Safety Review

The clinical research investigators are responsible for the initial evaluation and reporting of safety information at the participant level to the Protocol Chair. The Protocol Chair is responsible for alerting Gilead Sciences if unexpected concerns arise. Additional reviews may be conducted at each of these levels as dictated by the occurrence of certain events.

The Reproductive Infectious Disease Data Management team will review incoming safety data on an ongoing basis. Events identified as questionable, inconsistent, or unexplained will be queried for verification. The clinical investigator and two independent safety monitors (one obstetrician and one pediatrician) will communicate approximately every month, as applicable to review clinical data reports. The content, format and frequency of the clinical data reports will be agreed upon by the independent safety monitors and the study investigators in advance of study implementation. In addition to the routine safety data reviews, the independent safety

monitors and the study investigators will convene on an ad hoc basis to make decisions regarding the handling of any significant safety concerns. If necessary, external experts representing expertise in the fields of pregnancy, newborn medicine, infectious diseases, hepatology and medical ethics may be invited to join the safety review. A recommendation to pause or stop the trial may be made at this time or at any such time that the safety review team agrees that an unacceptable type and/or frequency of AEs has been observed.

To assist in consistent and efficient concomitant medication recording for inpatient admissions (delivery and serious adverse event), the UPMC Health Record Research Request (R3) service may be used to extract concomitant medications administered during any inpatient admission for maternal and infant study participants. If utilized, the extracted data will be provided to the study team in a format agreed upon by R3 and data management. Additional data may be extracted by R3 and/or the MOMI database to assist in data capture (i.e. APGARS, obstetric age, pregnancy outcomes).

8.3 Adverse Events Definitions and Reporting Requirements

8.3.1 Adverse Events

An AE is defined as any untoward medical occurrence in a clinical research participant administered an investigational medication and which does not necessarily have a causal relationship with the investigational medication. As such, an AE can be an unfavorable or unintended sign (including an abnormal laboratory finding, for example), symptom or disease temporally associated with the use of an investigational medication, whether or not considered related to the medication. The term “investigational medication” for this study refers to the study medication.

Study participants will be provided instructions for contacting the study site to report any untoward medical occurrences they may experience throughout their participation in the study. Participants receiving prenatal care and/or delivering at Magee-Womens Hospital will be instructed to come to Magee-Womens Hospital if they experience any adverse events requiring evaluation. Participants will be seen by a physician investigator/study clinician. If the participant is not receiving care at Magee-Womens Hospital, then they will be instructed to seek medical care with their local primary care physician/obstetrical team. Participants may have an unscheduled visit with the physician investigator/study clinicians as necessary or desired. In cases of potentially life-threatening events, participants will be instructed to seek immediate emergency care. With appropriate permission of the participant, whenever possible, records from all non-study medical providers related to untoward medical occurrences will be obtained and required data elements will be abstracted and recorded on study CRFs. All participants reporting an untoward medical occurrence will be followed clinically as deemed appropriate by a physician investigator until the occurrence resolves (returns to baseline) or stabilizes.

Study site staff will document AEs reported by or observed in enrolled study participants by severity and presumed relationship to investigational medication, including gradable laboratory findings. Medication from hospital admissions may be extracted from the medical record using the UPMC Health Record Research Request (R3) service and/or MOMI database to ensure consistency and accuracy of reporting.

Some of the study participants will have opioid use disorder (OUD) and may be prescribed either methadone or buprenorphine as treatment. Infants who are exposed to these medications often experience neonatal opioid withdrawal syndrome (NOWS). Given that this is an expected outcome for this treatment, we will not report this as an AE. All opioid exposed infants in the UPMC hospital system have at minimum a 5-day observation period and those who require pharmacologic treatment for NOWS can remain in the hospital for up to a month (mean 14 days). A study pediatrician, will review all NOWS related hospitalization records to ensure that there are no hospital events that are outside the scope of standard NOWS findings, for example pneumonia, sepsis, and hypoglycemia.

Additionally, certain adverse events are expected as a consequence of labor and delivery. Prior to delivery, expected pregnancy findings, such as lower extremity edema, physiologic discharge of pregnancy, and pain from contractions as determined by a study clinician will not be considered adverse events. During the postpartum period, expected pregnancy findings such as lower extremity edema, abdominal pain from uterine cramping, incisional pain from a cesarean section, perineal pain after vaginal delivery, and vaginal bleeding as determined by a study clinician will not be considered adverse events. Expected symptoms may be further defined and reported accordingly in a protocol specific standard operating procedure (SOP) or guidance document.

AE severity will be graded per the most current DAIDS Table for Grading Adult and Pediatric Adverse Events.

8.3.2 Serious Adverse Events

An SAE will be defined as an AE that:

- Results in death
- Is life-threatening
- Requires inpatient hospitalization or prolongation of existing hospitalization, except those that are expected such as hospitalization for neonatal opioid withdrawal syndrome.
- Results in persistent or significant disability/incapacity
- Is a congenital anomaly/birth defect
- Is an important medical event that may not result in death, be immediately life-threatening, or require hospitalization but may jeopardize the participant or require intervention to prevent one of the outcomes listed in the definition above.

8.3.3 Adverse Event Relationship to Study Medication

Relatedness is an assessment made by the physician investigator of whether or not the event is related to the study agent.

- *Related*: There is a reasonable possibility that the AE may be related to the study agent(s)
- *Not Related*: There is not a reasonable possibility that the AE is related to the study agent(s)

8.4 Expedited Adverse Event Reporting Requirements

8.4.1 Reporting Requirements for this Study

All adverse events will be reported to Gilead Sciences on a monthly basis. All serious adverse events that are considered unexpected and related to the study medication will be reported to the University of Pittsburgh Institutional Review Board, the FDA and Gilead Sciences according to their reporting guidelines.

8.4.2 Grading Severity of Events

The most current Division of AIDS Table for Grading the Severity of Adult and Pediatric Adverse Events (DAIDS AE Grading Table) is available on the RSC website at <http://rsc.tech-res.com/safetyandpharmacovigilance/>.

8.5 Regulatory Requirements

Information on all applicable AEs will be included in reports to the FDA and other applicable government and regulatory authorities. The Protocol Chair will submit AE information in accordance with the requirements of the University of Pittsburgh IRB.

8.6 Social Harms Reporting

Although every effort will be made to protect participant privacy and confidentiality, it is possible that participants' involvement in the study could become known to others and that social harms may result. Social harms that are judged by the study investigators to be serious or unexpected will be reported to Gilead Sciences and to the University of Pittsburgh IRB.

9 CLINICAL MANAGEMENT

Guidelines for clinical management and permanent discontinuation of study medication are outlined in this section. In general, the physician investigators will only discontinue study medication in consultation with the independent physician safety monitor(s) if they feel that the risk of study medication continuation outweighs the benefits of study medication continuation. The physician investigator(s) will document all permanent discontinuations on applicable CRFs.

9.1 Grading System

AE severity grading is described in Section 8.3.1.

9.2 Dose Modification Instructions

No dose modifications will be permitted in this study.

9.3 General Criteria for Permanent Discontinuation of Study Medication

A participant will be permanently discontinued from medication use by the physician investigator(s) for any of the following reasons, according the HCV treatment guidelines²³:

- 5-fold or greater increase in ALT or AST at the PK1 or PK2 visit compared to baseline result (Screening visit), confirmed by immediate repeat testing
- Any increase of ALT or AST of less than 5-fold from baseline (Screening visit) at the PK1 or PK2 visit that is accompanied by any weakness, nausea, vomiting, or jaundice
- 3-fold or greater increase in ALT or AST accompanied by bilirubin $>2x$ the upper limit of normal, confirmed on immediate repeat testing
- Increase HCV RNA viral load by greater than 10-fold at PK2 visit (6-8 weeks after starting treatment)
- Participant is unable or unwilling to comply with required study procedures
- If the participant delivers prematurely (and is still on study medication) and desires to breastfeed
- Participant might be put at undue risk to their safety and well-being by continuing medication use, according to the judgment of the study investigator(s). The study investigators will consult with the independent safety physician prior to all study medication discontinuation instituted for this reason.

Any time a participant is permanently discontinued from study medication (prior to completion of the 12 week course of study medication), HCV resistance testing will be performed.

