 - HCV RNA viral load will be assessed at 12 weeks after completion of SOF/VEL treatment. An undetectable viral load will be considered a SVR12.

- **Maternal Safety**
 - Safety laboratory assessments of blood counts, creatinine, liver function, creatinine kinase and lipase will be measured at the PK1 and PK2 visits (approximately 3 weeks and 6 weeks after treatment initiation).
 - Pregnancy and delivery outcomes collected prospectively by participant interview and medical record review.
- **Neonate Safety**
 - Major malformations, defined as structural abnormalities with medical, surgical or cosmetic importance;
 - Weight, length, and head circumference at birth, 8 weeks, 6 months and 12 months;
 - HCV RNA viral load at birth (as available), 1 to 3 months, at 6 months and then again at 12 months only if negative viral loads are not documented at 1 to 3 and 6 months;
 - Neurodevelopmental assessments at 6 months and 12 months.

Exploratory Objectives:

- Describe the perspectives of pregnant women with chronic HCV infection screening for a trial of antenatal sofosbuvir/velpatasvir (SOF/VEL) therapy

Exploratory Endpoint:

- In depth interviews conducted before enrollment in screened participants and after completion of treatment in enrolled participants.

Table 1: Study Visit Schedule

	Maternal Study Visit	Target windows [†]
V1	Screening	14+0 to 22+6 weeks gestation (weeks + days)
V2*	Enrollment	23+0 to 25+6 weeks gestation (weeks + days)
V3	PK1: Intensive	3 weeks \pm 7 days after first dose of SOF/VEL
V3a [^]	PK1a, 24hr sample	24 hours \pm 2 hours
V4	PK2: Sparse	6 weeks \pm 7 days after first dose of SOF/VEL
V5	PK3: Intensive	9 weeks \pm 7 days after first dose of SOF/VEL
V5a [^]	PK3a, 24hr sample	24 hours \pm 2 hours
V6	End of Treatment	Within 7 days of SOF/VEL completion
Del**	Delivery	
V7/iV1	Post treatment	12 weeks \pm 4 days after completion of therapy
	Infant Study Visit	Infant Age
Del**	Delivery	Newborn
V7/iV1	Infant Visit 1	8 weeks \pm 6 weeks [†]
iV2	Infant Visit 2	6 months \pm 2 weeks [†]
iV3	Infant Visit 3	12 months \pm 2 weeks [†]

[†]These are target windows. If the participant cannot be seen within these windows then it will not be considered a protocol deviation.

*Start SOF/VEL and continue for 12 weeks

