5.3 Exclusion Criteria

Women who meet any of the following criteria will be excluded from the study:

- 1) Participant report of any of the following at Screening or Enrollment:
 - a. Previous treatment for Hepatitis C virus with sofosbuvir or a NS5A inhibitor
 - b. Use of any medications contraindicated with concurrent use of velpatasvir or sofosbuvir according to the most current EPCLUS³⁴ package insert³⁴
 - c. Plans to relocate away from the study site area in the next 1 year and 4 months and unable/unwilling to return for study visits
 - d. Current sexual partner is known to be infected with HIV or Hepatitis B virus
 - e. History of cirrhosis documented or reported by previous liver biopsy or liver imaging tests
- 2) Reports participating in any other research study involving investigational drugs or medical devices within 60 days or less prior to Enrollment
- 3) Clinically significant and habitual non-therapeutic drug abuse, not including marijuana, as determined by Protocol Chair
- 4) At Screening or Enrollment, as determined by the Protocol Chair, any significant uncontrolled active or chronic cardiovascular, renal, liver (such as evidence of decompensated cirrhosis by ascites, encephalopathy, or variceal hemorrhage), hematologic, neurologic, gastrointestinal, psychiatric, endocrine, respiratory, immunologic disorder or infectious disease (other than Hepatitis C)
- 5) Has a high risk of preterm birth defined as a history of spontaneous preterm birth at less than 34 weeks of gestation or a shortened cervical length of less than 20 millimeters
- 6) Has any of the following laboratory abnormalities at Screening:
 - a. Aspartate aminotransferase (AST) or alanine transaminase (ALT) greater than 10 times the upper limit of normal
 - b. Hemoglobin less than 9 g/dL
 - c. Platelet count less than 90,000 per mm³
 - d. International normalized ratio (INR) > 1.5

- e. Creatinine greater than 1.4
- 7) Has any other condition that, in the opinion of the IoR/designee, would preclude informed consent, make study participation unsafe, complicate interpretation of study outcome data, or otherwise interfere with achieving study objectives.

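### The ALT/AST stopping rules in Section 9.3 compare with a Screening value taken 1 to 83 days before the first dose, so a pre-treatment change counts as change on drug

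*Combined protocol and SAP*

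**What the plan says.** Section 9.3 opens with: "A participant will be permanently discontinued from medication use by the physician investigator(s) for any of the following reasons". Three of its criteria concern ALT or AST.

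- **5-fold rule:** a "5-fold or greater increase in ALT or AST at the PK1 or PK2 visit compared to baseline result (Screening visit"), confirmed by an immediate repeat.
- **Symptom rule:** "Any increase of ALT or AST of less than 5-fold from baseline (Screening visit) at the PK1 or PK2 visit" when weakness, nausea, vomiting or jaundice is also present. There is no minimum rise and no repeat test.
- **Bilirubin rule:** a "3-fold or greater increase in ALT or AST accompanied by bilirubin" above twice the upper limit of normal (ULN), confirmed by repeat. No baseline is named.

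Table 1 (Study Visit Schedule) puts Screening at "14+0 to 22+6 weeks gestation (weeks + days") and Enrollment, when the drug starts, at "23+0 to 25+6 weeks gestation (weeks + days"). Table 4 (Enrollment) lists HCV RNA as the only blood test. Appendix I schedules the hepatic panel at Screening, V3 (PK1), V4 (PK2) and V7, and leaves the Enrollment column blank.

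Sections 5.2 and 7.2 allow screening laboratories to be repeated before enrollment if there is concern. They do not make this routine, and no text says that a repeat becomes the Section 9.3 baseline.

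**The concern.** A rule that stops a drug for liver injury should measure change since the drug began. Here the comparison can start weeks earlier, so whatever ALT or AST did before the first tablet is included. There are two consequences.

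- **Pre-dose rise.** It counts towards a stop that the drug did not cause. The symptom rule is the easiest to meet this way: a small pre-dose rise that persists to PK1 or PK2, together with nausea, is enough. Section 2.2 itself lists nausea and vomiting among the changes of pregnancy.
- **Pre-dose fall.** It raises the on-drug increase needed to reach 5-fold, so the rule fires later than its wording suggests.

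A wrong stop is costly for the woman. It is permanent, Section 9.2 permits no dose modification, and Section 13.3.1 names resistance as a risk of an incomplete course. Under Sections 10.3 and 10.5.2 she is also replaced and left out of the SVR12 analysis.

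**Working it through.** The plan states no interval and no error rate for these rules, so there is no figure to reproduce. Two things can be worked out: the planned interval, and how a pre-dose change alters each rule.

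**Interval from Screening to first dose** (Table 1 windows, gestational age in days = 7 × weeks + days)

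- Shortest: 23+0 minus 22+6 = 161 − 160 = 1 day.
- Longest: 25+6 minus 14+0 = 181 − 98 = 83 days.

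**Interval from baseline to the on-treatment test** (PK1 at 3 weeks ± 7 days, so 14 to 28 days; PK2 at 6 weeks ± 7 days, so 35 to 49 days)

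| | From Screening | From Enrollment |
|---|---|---|
| PK1 | 1 + 14 = 15 to 83 + 28 = 111 days | 14 to 28 days |
| PK2 | 1 + 35 = 36 to 83 + 49 = 132 days | 35 to 49 days |

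**Effect on the rules.** Let q = pre-dose ALT ÷ Screening ALT, and r = on-treatment ALT ÷ pre-dose ALT. The plan compares on-treatment ALT with Screening ALT, which is q × r.

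- 5-fold rule: q × r ≥ 5, so the on-drug change needed is r ≥ 5/q.
- Symptom rule: 1 < q × r < 5, so any r above 1/q counts as an increase (up to 5/q, where the 5-fold rule takes over).
- With an Enrollment baseline the 5-fold rule is r ≥ 5, which is 5q times the Screening value.

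The documents give no q. The values below are assumed, to show the range.

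| Assumed q | On-drug change needed for 5-fold rule (5/q) | Symptom rule counts an increase when r exceeds (1/q) | Trigger with Enrollment baseline, as a multiple of Screening (5q) |
|---|---|---|---|
| 0.5 | 10 | 2 | 2.5 |
| 0.8 | 6.25 | 1.25 | 4 |
| 1 | 5 | 1 | 5 |
| 1.25 | 4 | 0.8 | 6.25 |
| 2 | 2.5 | 0.5 | 10 |

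With no change on drug (r = 1), the 5-fold rule is met only if q is at least 5. The laboratory part of the symptom rule is met for any q above 1 and below 5. Repeat testing, where required, confirms the on-treatment value; it cannot correct an old baseline.

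**The case against.** **No harm is demonstrated.** This stands. Elapsed time is not ALT drift, and the documents report no drift between 14 and 26 weeks. A reader might infer from the 83-day maximum that a sizeable share of women will be wrongly stopped. The documents do not support that. How long before dosing the baseline was taken is not an error rate, and a stop under the 5-fold rule with no drug effect needs a 5-fold pre-dose rise, confirmed on repeat.

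**A delayed stop is largely backed up.** This mostly stands. Section 9.3 has an undue-risk criterion based on judgement. Abnormal laboratory findings are adverse events (8.3.1), and 9.4 stops the drug for related Grade 3 or 4 events. Two independent physicians review safety data monthly or more often (8.1). A reader might infer that liver injury would go unnoticed; these routes do not depend on the Screening value. They do call for judgement about risk or relatedness, and no routine pre-dose panel is there to inform it.

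**Clinical judgement governs stopping.** In part. Section 9 begins: "In general, the physician investigators will only discontinue study medication in consultation with the independent physician safety monitor(s"), on a weighing of risk against benefit. Yet 9.3 is worded as mandatory, and within it only the undue-risk criterion repeats the duty to consult. The plan does not say which text prevails.

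**Repeat screening laboratories already help.** In part. A repeat could be read as the updated Screening result, but it depends on someone having a concern, and the plan does not say that it replaces the earlier value.

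**A later baseline has its own drawback.** True. If ALT doubles before dosing, the 5-fold trigger moves from 5 to 10 times the Screening value. The review step in the fix is there for that case.

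**Conclusion.** The point holds as an inexpensive improvement to a safety rule. Two of the three ALT/AST rules use a baseline that may be up to 83 days older than the first dose, the third has none, and no routine panel is taken just before treatment. Pre-dose change is therefore counted as on-drug change. The false-stop side matters more, chiefly through the symptom rule; other provisions largely cover the delayed-stop side.

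The 1-to-83-day range follows from the target windows, and a visit outside them is not a deviation. The fold figures rest on assumed values of q. The frequency of a wrong or delayed stop cannot be computed and is probably small in 10 women.

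Two further inferences go beyond the documents. The first is that the primary PK comparison is compromised: the only link shown is replacement of women who stop early, which follows any early stop. The second is that a new baseline would secure the symptom rule. It would not, because with no minimum rise, ordinary variation can still meet the laboratory part of that rule under either baseline.

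**What to change.** 1. Add the hepatic panel to the Enrollment (V2) blood draw, before the first tablet, in Table 4 and Appendix I.
2. In Section 9.3, define baseline for all three ALT/AST rules as the last value before the first dose: the V2 value or, if it is missing, the most recent earlier one.
3. Keep eligibility at Screening, where "Aspartate aminotransferase (AST) or alanine transaminase (ALT) greater than 10 times the upper limit of normal" excludes. Dispensing need not wait for the V2 result. State that a V2 ALT or AST above 10 times ULN, once reported, leads to prompt repeat testing and safety-monitor review of whether to continue. Without this step, a woman with such a value would have a 5-fold trigger above 5 × 10 = 50 times ULN.

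The gap from baseline to first dose then falls to 0 days when the V2 panel is available. The cost is a few extra tests in about 10 women at a draw already planned, some wording, and a higher absolute trigger when ALT rises before dosing. Whether the symptom rule should have a minimum rise is a separate clinical choice.
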